5.6 Exposure to Investigational Product

Exposure to investigational product for the Safety Set will be summarized in terms of treatment duration, which is calculated as the number of days from the date of first dose of investigational product taken to the date of the last dose of investigational product taken, inclusively. Descriptive statistics (number of subjects, mean, standard deviation, minimum, median, and maximum) will be presented to describe the exposure to investigational product.

A listing will be created by subject number and visit giving the date and time of dose administration for the Safety Set.

5.7 Measurements of Treatment Compliance

This is a study in which the investigational products will be administered from Day 1 to Day 8 at the study site only (in-house confinement treatment period). All compliance related data will be included in the exposure data listing. No separate treatment compliance summary or data listing will be provided.

5.8 Protocol Deviations

Protocol deviations will be recorded by the site separately from the clinical database. Protocol deviations will be classified as major or minor per the agreed protocol deviation management plan. The Shire study team will review the protocol deviations and their classification throughout the study and before database lock.

Decisions of the review will include categorization of major and minor protocol deviations.

Confirmed major and minor protocol deviations will be documented in the protocol deviation tracker for the study. Major/minor protocol deviations will be summarized by category for the Safety Set. Major/minor protocol deviations will be listed for the Enrolled Set.

6. EFFICACY ANALYSES

Not applicable.

7. SAFETY ANALYSIS

The safety analysis will be performed using the Safety Set. Safety parameters include AEs, clinical laboratory results, vital signs, and ECG results. For each safety parameter, the last value collected prior to dosing on Day 1 will be used as baseline for all analyses of that safety parameter.

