**Table 3: Schedule of Assessments – Detail of Treatment Period Day 8**

Study Procedure/Relative to IP Administration	Administration of Anagrelide & Omeprazole a	Anagrelide PK Sample Collection	Omeprazole PK Sample Collection	Physical Examination	Vital Signs b (BP and pulse)	12-lead ECG b	Biochemistry, hematology, and urinalysis	Concomitant Medications	Adverse Events/Serious Adverse Events
Pre-dose c		X	X		X	X	X	X	X
0	X d							X	X
0.5 hours		X	X					X	X
1 hour		X	X		X			X	X
1.5 hours		X	X					X	X
2 hours		X	X		X			X	X
2.5 hours		X	X					X	X
3 hours		X	X					X	X
4 hours		X	X		X			X	X
8 hours		X	X		X			X	X
12 hour		X	X		X	X		X	X
24 hour			X	X	X	X	X	X	X

ECG=electrocardiogram; PK=pharmacokinetic; IP=Investigation Product

a The subjects should be administered anagrelide and omeprazole concurrently starting at 8:00 am.

b Subjects should be resting in a supine position for at least 5 minutes prior to collecting vital signs and ECGs.

c Pre-dose assessments should be performed within 30 minutes prior to dose.

d Subjects are required to fast for approximately 10 hours prior to and until 4 hours post-dose (after PK and safety assessments) on Days 1 and Day 8.

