#### 1.2.1 Clinical Information

Anagrelide administered to healthy subjects during Phase 1 clinical studies demonstrated a consistent safety profile at 1mg/day dosing. In studies SPD422-107 and SPD422-110, there were no serious adverse events. Treatment-emergent events were primarily mild, and the most common events (>10%) were dizziness, postural dizziness, headache, feeling hot, procedural site pain, and palpitations. There were no clinically significant electrocardiogram (ECG) changes reported in either study. In healthy subjects receiving a single dose of anagrelide 2.5mg (study SPD422-111, Thorough QT study), 73% of subjects reported headache, and >20% of subjects reported dizziness and nausea. One subject was withdrawn from the study due to treatment-emergent T-wave inversion on ECG at the 2.5 mg dose. In that study, the high dose of anagrelide 2.5 mg rapidly increased mean heart rate during the first 1.5 hours after administration, with the largest mean time-matched increase of +29.1 bpm occurring at 2 hours after administration.

Additionally, anagrelide 2.5 mg increased the QTcNi (patient-specific corrected QT) and QTcF (Fridericia corrected QT) with an upper 2-sided 90% confidence interval (CI) exceeded 10msec at 1 and 1.5 hours (values of 15.7 msec and 13.6 msec, respectively) for QTcNi and at 1 hour for QTcF (value of 12.7 msec). These changes corresponded to the time of  $t_{max}$  for anagrelide and its active metabolite, 3-hydroxy-anagrelide, and the magnitude of the change at these time points met the definition for a positive thorough QT study. However, the QTcNi and QTcF values were increased only when the heart rate was increasing rapidly at 0.5-1.5 hours after administration of anagrelide 2.5mg, and the interpretation of the increased QTcNi and QTcF may be confounded by the rapid increase in heart rate and the corresponding QT-RR hysteresis that occurs when the heart rate changes rapidly.

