### 3.1.3 Treatment Period (Day 1-9)

Subjects will be admitted to the CRC after eligibility is confirmed on Day -1. Subjects will be confined at the CRC from Day -1 until after completion of the 24 hour post dose assessments on the morning of Day 9. Administration of study drug on Days 1-8 should be at the same time each morning for each subject during the study.

Study procedures, safety and pharmacokinetic assessments will be collected and reported at scheduled time points during the study. The timing of these assessments are described in [Table 1](#), [Table 2](#), and [Table 3](#).

Day 1: Anagrelide 1 mg, (administered orally as two 0.5 mg capsules) will be administered to all study subjects at approximately 8:00 in the morning on Day 1. Subjects are required to fast for 10 hours prior to and until 4 hours following administration of anagrelide on Day 1.

Days 2-7: Omeprazole 40 mg will be administered orally QD on Days 2-7 to all subjects. Omeprazole will be administered at approximately 8:00 in the morning, prior to breakfast.

Day 8: Anagrelide 1 mg and omeprazole 40 mg will be administered concurrently to all subjects at approximately 8:00 in the morning on Day 8. Subjects are required to fast for 10 hours prior to and until 4 hours following administration of anagrelide and omeprazole on Day 8.

Day 9: Subjects will be discharged from the CRC on Day 9 following the completion of all study procedures and assessments.

Subjects who discontinue early from the study will complete the Early Termination assessments.

- Safety Assessments include but are not limited to assessment of adverse events, physical examinations, 12-lead ECG, vital signs (blood pressure and pulse) and safety laboratory tests (hematology, chemistry, and urinalysis).
- Pharmacokinetic assessments:
  - Omeprazole: plasma concentrations of omeprazole
  - Anagrelide: plasma concentrations of anagrelide, 3-hydroxy-anagrelide and RL603

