### 4.3 Restrictions

1. Subjects should refrain from strenuous physical exercise 48 hours prior to admission to the CRC and during the in-house stay at the CRC.
2. Subjects should refrain from alcohol 48 hours prior to admission to the CRC and during the in-house stay at the CRC.
3. Subjects should refrain from foods or beverages containing caffeine/xanthine 48 hours prior to admission to the CRC and during the in-house stay at the CRC.
4. On Day 1 and Day 8 subjects will be required to fast for approximately 10 hours prior to administration of investigational product and continuing through 4 hours after administration. In addition, water intake will be restricted (except for water to administer the dose) starting 4 hours prior and continuing up to 2 hours after administration of the investigational product.
5. Subjects will be required to follow standardized meal schedules and eat the meals provided by the site while housed in the CRC. No outside food or beverages (including gum, mints, etc.) will be permitted. Menus will be identical for all subjects at the CRC. Copies of the menus will be provided to the sponsor for approval prior to the start of the study. While confined, the total daily nutritional composition should be approximately 50% carbohydrate, 35% fat, and 15% protein. The daily caloric intake per subject should not exceed approximately 3200 kcal.

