### 7.2.2.9 Electrocardiogram

Twelve-lead ECGs will be performed at the times specified in [Table 1](#), [Table 2](#), and [Table 3](#) using the standard methods/equipment at the CRC.

The following parameters will be recorded on the appropriate CRF page: heart rate, PR, RR, QRS, and QT intervals. The QTcB and QTcF will be derived from the data in the database. The investigator's assessment of the ECG tracing as normal or abnormal must be documented, and if abnormal, his/her determination of whether the abnormality is clinically significant or not will be documented on the tracing and recorded in the CRF.

The subject should be asked to remove all clothing that covers the location of lead placement. The subject must be resting in the supine position for at least 5 minutes prior to collecting the ECG.

In some cases, it may be appropriate to repeat abnormal ECGs to rule out improper lead placement as contributing to the ECG abnormality. It is important that leads are placed in the same positions each time in order to achieve precise ECG recordings.

One complete recording, including a 10-second rhythm strip, should be taken at each time point. It should be immediately assessed as a valid recording and if not valid, it should be repeated. Invalid recordings will not be entered in the CRF. The ECG collected predose on Day 1 will serve as the subject's baseline ECG.

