## 9.9 Safety Analyses

The safety endpoints will be summarized with descriptive statistics for the safety set.

Relevant safety endpoints as well as their changes from baseline will be summarized. Baseline is defined as the last assessment prior to the first dose of investigational product. Potentially clinically important findings will also be summarized or listed. The potentially clinically important values will be defined in the SAP.

Adverse events will be coded using the Medical Dictionary for Regulatory Activities. The number of events, incidence, and percentage of treatment-emergent adverse events will be calculated overall, by system organ class, by preferred term, and by treatment group. Treatment-emergent adverse events will be further summarized by severity and relationship to investigational product. Adverse events related to investigational product, AEs leading to withdrawal, SAEs, and deaths will be similarly summarized/listed.

Safety will be assessed by treatment emergent adverse events (TEAEs), new findings from physical examination, evaluation of blood pressure, heart rate, new findings from 12-lead ECG, and clinical laboratory test results (biochemistry, hematology, and urinalysis).

Clinical laboratory tests, vital signs, and ECG findings will be summarized by treatment group and visit. Potentially clinically important findings will also be summarized or listed.

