11.2 Definition of Baseline

Baseline for all safety analyses is defined as the last observed value for the safety assessment prior to taking the first dose of investigational product on Day 1 (based on dates or date/times).

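### Day 8 changes in pulse and blood pressure are taken only from the Day 1 baseline, so the combination and anagrelide-alone columns are not like for like

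*SAP*

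**What the plan says.** Both documents fix a single baseline.

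- SAP 7: "the last value collected prior to dosing on Day 1 will be used as baseline for all analyses of that safety parameter".
- SAP 11.2 repeats it as "the last observed value for the safety assessment prior to taking the first dose of investigational product on Day 1".
- Protocol 9.9: "Baseline is defined as the last assessment prior to the first dose of investigational product".
- Protocol 7.2.2.9, for ECG: "The ECG collected predose on Day 1 will serve as the" baseline for each subject.

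SAP 7.3 summarises blood pressure and pulse, and their changes from that baseline, by treatment group. The PCI criteria in SAP Table 2 use the same baseline. A high pulse, for example, needs a value of at least 100 bpm together with a rise of more than 15 bpm.

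Between the two anagrelide doses, "Omeprazole 40 mg will be administered orally QD on Days 2-7 to all subjects" (Protocol 3.1.3). On Day 8 the schedule calls for vital signs before dosing as well as after, and "Pre-dose assessments should be performed within 30 minutes prior to dose" (Protocol Table 3; SAP Table 6 agrees). Neither document uses that reading as a reference value. SAP 7.5 and 9 plan no further safety or other analyses, and SAP 13 records no change from the protocol.

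**The concern.** The secondary objective covers the safety of anagrelide, omeprazole and the two together, and the tables will set the treatments side by side. Heart rate is the drug's documented acute effect: after 2.5 mg, Protocol 1.2.1 reports a rapid rise "with the largest mean time-matched increase of +29.1 bpm occurring at 2 hours after administration". A reader of the vital-sign tables will naturally look at the post-dose rise on Day 1 and on Day 8 and ask whether omeprazole altered it.

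The planned columns do not answer that question cleanly. The Day 1 rise is measured from a reading minutes before the dose. The Day 8 rise is measured from a reading a week earlier. Any change in resting level over that week appears in the combination column and nowhere else. With one sequence and no control arm, nothing cancels it.

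**Working it through.** The plan states no figure to reproduce here. The check is an identity, followed by an illustration.

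**Inputs from the documents**

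- Pulse and blood pressure on Day 1: pre-dose and 1, 2, 4, 8 and 12 hours (Protocol Table 2).
- On Day 8: the same times plus 24 hours (Protocol Table 3).
- No vital signs are scheduled on Days 2 to 7 (SAP Table 4). Day 8 pre-dose is therefore the only scheduled vital-sign reading after omeprazole has started and before the second anagrelide dose.
- Omeprazole doses before the Day 8 pre-dose reading: one a day on Days 2 to 7, which is 6.

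**Identity.** Write Y1pre and Y8pre for the pre-dose readings, and Y1(t) and Y8(t) for the readings t hours after the dose.

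- Day 1 change as planned: Y1(t) − Y1pre.
- Day 8 change as planned: Y8(t) − Y1pre = [Y8(t) − Y8pre] + [Y8pre − Y1pre].

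The first bracket is the within-day change after the combination. The second is the pre-dose shift S. The Day 1 change has no such term, so the difference between the columns is the difference in within-day changes plus S. This needs no assumption.

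**What existing summaries can recover.** If the Day 8 pre-dose row is tabulated and the same subjects contribute, subtracting mean changes gives the mean within-day change. The standard deviation does not follow, because Var[Y8(t) − Y8pre] depends on the covariance of the two changes, which is not reported. Change-based PCI counts do not follow either, because they are decided subject by subject.

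**Illustration. All inputs are assumed; none comes from the documents.** True within-day pulse rise 5 bpm on both days; SD of a single reading 5 bpm; SD of individual shifts 4 bpm; mean shift −6 to +6 bpm; normal distributions.

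- From Day 8 pre-dose: mean 5.0, SD √(5² + 5²) = 7.07. Share with a rise above 15 bpm: P(Z > (15 − 5)/7.07) = P(Z > 1.41) ≈ 8%, whatever the shift.
- From the Day 1 baseline: mean 5 + shift, SD √(5² + 5² + 4²) = 8.12.

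| Mean shift (bpm) | Mean Day 8 change from Day 1 baseline | (15 − mean)/8.12 | Share with rise above 15 bpm |
|---|---|---|---|
| −6 | −1.0 | 1.97 | about 2% |
| −3 | 2.0 | 1.60 | about 5% |
| 0 | 5.0 | 1.23 | about 11% |
| +3 | 8.0 | 0.86 | about 19% |
| +6 | 11.0 | 0.49 | about 31% |

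The acute effect is the same in every row. Even at zero mean shift the share differs (11% against 8%), because individual shifts add spread. In 20 subjects, 8% and 19% are 1.6 and 3.8 people. These shares are not PCI rates, since the pulse rule also requires a value of at least 100 bpm.

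**The case against.** The single baseline is pre-specified, consistent across both documents and matches the stated endpoint. It is also the only untreated reference. A change from Day 8 pre-dose removes any sustained omeprazole contribution, which is part of what the combination does to a subject. All of this stands, and it is why the Day 1 baseline should be kept.

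Much of the information is also within reach. All vital signs are listed, and means can be subtracted where the Day 8 pre-dose row is shown. The table layouts are in a separate document that is not available here. That lowers the stakes, but it does not supply the within-day SDs or PCI counts. SAP 7.3 also promises vital-sign changes by visit, with only the PCI counts by time point.

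Several stronger readings are tempting, and the documents do not support them.

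- *The plan makes a biased treatment comparison.* The secondary objective is to assess each treatment, and safety is descriptive, with no test or interval. Any difference would be a reader's inference.
- *The shift is a large share of the drug effect.* Scaling 29.1 bpm to 1 mg gives 29.1 × 1/2.5 = 11.6 bpm, and an assumed shift of 3 to 5 bpm would be 26% to 43% of it. Both dose proportionality and the shift are assumptions, so the percentage is not evidence.
- *Stopping caffeine drives the shift.* Subjects must "refrain from foods or beverages containing caffeine/xanthine 48 hours prior to admission to the CRC and during the in-house stay" (Protocol 4.3), and admission is on Day −1, so abstinence already applies at both pre-dose readings.
- *The acute ECG effect is obscured.* Post-dose ECGs are taken only at 12 hours, and at 24 hours on Day 8. The changes described in Protocol 1.2.1 occur within about 2 hours, so neither baseline would show them.
- *The shift measures omeprazole.* In a single-sequence design, it cannot be separated from time and confinement.

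**Conclusion.** The concern holds for pulse and blood pressure. Against the Day 1 baseline, the Day 8 combination change contains the whole Day 1 to Day 8 pre-dose shift, and the Day 1 anagrelide-alone change contains none of it. The one-for-one transfer into the mean is exact. The size and direction of the shift cannot be derived from the documents, and the illustration shows only how sensitive a change-based count could be under assumed values.

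There is a related gap. SAP 7.1 assigns adverse events just before the Day 8 anagrelide dose to omeprazole alone, but SAP 7.3 gives no rule for the treatment group of the Day 8 pre-dose vital signs.

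This is a worthwhile, inexpensive improvement to a descriptive secondary analysis. The Day 1 baseline is not an error.

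**What to change.** - Keep the Day 1 baseline for all safety analyses.
- In SAP 7.3, add the change from Day 8 pre-dose for Day 8 post-dose pulse and blood pressure, with change-based PCI counts on the same reference. Show it beside the Day 1 change from Day 1 pre-dose at 1, 2, 4, 8 and 12 hours.
- Show Day 8 pre-dose minus Day 1 pre-dose as its own row. Assign it to the omeprazole-alone period, in line with the adverse-event rule in SAP 7.1, and note that omeprazole, time and confinement effects cannot be separated.
- The same column may be added for ECG in SAP 7.4, with a note that the ECG schedule will not show an early effect.

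The cost is an extra column and row in planned tables, with no new data. The downsides are two change scores that need clear labels, and a second score that excludes any sustained omeprazole effect, which its footnote should say.

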7.1 Adverse Events

Adverse events will be coded using MedDRA Version 21.1.

An AE (classified by PT) will be considered a treatment-emergent AE (TEAE) if it starts on or after dosing on Day 1, or if it starts before dosing on Day 1 but increases in severity on or after dosing on Day 1 through the end of the study. If more than 1 AE with the same PT is reported before dosing on Day 1, then the AE with the greatest severity will be used as the benchmark for comparison to the AEs occurring after dosing on Day 1 under the PT.

Treatment most recently taken when the AE occurred will be used for the summaries:

- Any AE that started (or increased in severity) on or after the administration of anagrelide on Day 1, but before the administration of omeprazole on Day 2 will be assigned to anagrelide alone;
- Any AE that started (or increased in severity) on or after the administration of omeprazole on Day 2, but before the administration of anagrelide on Day 8 will be assigned to omeprazole alone;
- Any AE that started (or increased in severity) on or after the administration of anagrelide on Day 8 will be assigned to anagrelide with omeprazole.

An overall summary of the number of subjects with TEAEs as well as the number of events will be presented by treatment group, including the number and percentage of subjects with any TEAEs, serious TEAEs, TEAEs related to investigational product, serious TEAEs related to investigational product, TEAEs leading to discontinuation of investigational product, serious TEAEs leading to discontinuation of investigational product, TEAEs leading to discontinuation from study, serious TEAEs leading to discontinuation from study, severe TEAEs, TEAEs leading to hospitalization, and TEAEs leading to death.

The number and percentage of subjects reporting TEAEs, as well as the number of events, in each treatment group and overall will be tabulated by SOC and PT, and by SOC, PT, and maximum severity. The TEAEs considered related to investigational product will also be summarized by SOC and PT. If more than 1 AE occurs with the same PT, after the same treatment for the same subject, then the subject will be counted only once for that treatment group and PT using the most severe and most related occurrence for the summarization by severity and by relationship to investigational product. Summaries by SOC and PT will present SOC sorted alphabetically and PT within SOC by descending incidence.

The TEAEs and related TEAEs will be summarized by PT by descending frequency. Serious TEAEs, TEAEs leading to discontinuation of investigational product and serious TEAEs leading to death, will be summarized by SOC, PT, and treatment group.

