1. INTRODUCTION

This statistical analysis plan (SAP) provides a technical and detailed elaboration of the statistical analyses of pharmacokinetic (PK) and safety data described in the original study protocol dated 04 Oct 2018. Specifications for tables, figures, and listings (TFLs) are contained in a separate document (SPD422-113 TFL Shells).

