5.5 Concomitant Medications

Concomitant medications will be coded using the WHO Drug Dictionary Enhanced Version dated 01 September 2018.

Concomitant medication is defined as any medication with a start date prior to the date of the first dose of investigational product and continuing after the first dose of investigational product or with a start date between the dates of the first and last doses of investigational product, inclusive. Any medication with a start date after the date of the last dose of investigational product will not be considered a concomitant medication.

Concomitant medication usage will be summarized by the number and proportion of subjects receiving each medication by PT, by treatment group and overall, for the Safety Set. Multiple medication usage by a subject in the same category will be counted only once. Concomitant medications will be assigned to the treatment(s) with which they are concomitant. A medication is concomitant with a treatment if the subject received that medication any time between the time when that treatment was received and when the next treatment was received, or in the case of the last treatment, until the end of the

follow-up period. Therefore, a medication may be concomitant with more than one treatment.

All concomitant medications will be listed for the Safety Set.

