7.3 Vital Signs

Descriptive statistics for vital signs (systolic and diastolic blood pressure and pulse rate) and their changes from baseline at each post-baseline visit and at end of study will be presented by treatment group.

Vital sign values will be considered PCI if they meet both the observed value criteria and the change from baseline criteria listed in Table 2. The number and percentage of subjects with PCI post-baseline values will be tabulated by time point and treatment group. The percentages will be calculated relative to the number of subjects with baseline and available assessment at that time point in that treatment group. The numerator is the total number of subjects with at least 1 PCI post-baseline vital sign value at that time point in that treatment group. A supportive listing of subjects with post-baseline PCI values will be provided including the subject number, baseline, and post-baseline PCI values.

Table 2: Criteria for Potentially Clinically Important Vital Signs

Parameter	Classification	Criteria
Sitting and Supine		
Systolic BP (mmHg)	LOW and DECREASE	≤90 and decrease of ≥20 from baseline value
	HIGH and INCREASE	≥140 and increase of ≥20 from baseline value
Diastolic BP (mmHg)	LOW and DECREASE	≤50 and decrease of ≥15 from baseline value
	HIGH and INCREASE	≥90 and increase of ≥15 from baseline value
Pulse rate (bpm)	LOW and DECREASE	≤45 and decrease of >15 from baseline value
	HIGH and INCREASE	≥100 and increase of >15 from baseline value
Temperature (regardless of method)	LOW	<35°C or <95°F
	HIGH	>38.3°C or >100.9°F
Respiratory rate (breaths/min)	LOW	<10
	HIGH	>25

Abbreviations: BP=blood pressure, bpm=beats per minute.

All vital signs data will be listed for the Safety Set.

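### The anagrelide-alone TEAE column covers about 24 hours and the combination column 5 to 9 days, so the two are not like for like in the safety description

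*SAP*

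**What the plan says.** SAP 7.1 builds three columns from dose times. An event that begins or worsens from the Day 1 anagrelide dose onward "but before the administration of omeprazole on Day 2 will be assigned to anagrelide alone". From the Day 2 omeprazole dose the next column applies, "but before the administration of anagrelide on Day 8 will be assigned to omeprazole alone". The last column has a start and no stated end: "Any AE that started (or increased in severity) on or after the administration of anagrelide on Day 8 will be assigned to anagrelide with omeprazole".

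The end comes from the protocol. Protocol 8.1 collects adverse events up to the follow-up contact, which Protocol 3.1.4 and 7.1.3 place 7±2 days after the last dose. Protocol 3.1.3 keeps subjects in the unit until the 24-hour assessments on the morning of Day 9.

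On reporting, SAP 7.1 states: "The number and percentage of subjects reporting TEAEs, as well as the number of events, in each treatment group and overall will be tabulated". It adds: "The TEAEs considered related to investigational product will also be summarized by SOC and PT". Neither SAP 7.1 nor Protocol 9.9 sets a common window, a time denominator or a label giving window length. SAP 5.6 summarises exposure only as overall treatment duration. Table layouts are held elsewhere: "Specifications for tables, figures, and listings (TFLs) are contained in a separate document (SPD422-113 TFL Shells". That document was not available.

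**The concern.** The secondary objective is the safety and tolerability of anagrelide, of omeprazole and of the two together. The by-treatment TEAE tables are the main adverse event display for it, and they set the combination next to anagrelide alone. A reader will naturally compare those two columns, but one is open for 4 to 8 more days.

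The handling of delayed events adds a second asymmetry that does not depend on any background rate. An event starting 30 hours after the Day 1 dose is counted under omeprazole alone. The same event 30 hours after the Day 8 dose stays under the combination.

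The way events are found also differs. The anagrelide-alone window is wholly in-house, whereas most of the combination window follows discharge and is covered by one contact.

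What is at stake is the descriptive reading of the secondary objective, and nothing beyond that.

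**Working it through.** **Follow-up length.** The documents state no length for any TEAE window. The one stated figure that depends on follow-up is the maximum participation of about 46 days (Protocol 3.2). Screening 28 + treatment 9 + follow-up 9 (7 + 2) = 46, so 9 days is confirmed as the longest follow-up.

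**Windows, for a subject who takes every dose.** Doses are given at about 08:00 (Protocol 6.2.2).

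- Anagrelide alone: Day 1 08:00 to Day 2 08:00 = 24 h.
- Omeprazole alone: Day 2 08:00 to Day 8 08:00 = 144 h, or 6 days.
- Combination: Day 8 08:00 to follow-up = 120 to 216 h, or 5 to 9 days.

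**Assumed rates.** Protocol 1.2.1 says that the most common events at 1 mg/day each exceeded 10%, and it gives figures for a 2.5 mg dose. It gives no any-TEAE rate at 1 mg and no background rate. The following are therefore assumptions:

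- acute risk per anagrelide dose, a = 0.20 to 0.40;
- background risk per day, h = 0.01 to 0.05;
- share of background events judged related, r = 0.10 to 0.25.

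There is no omeprazole or period effect. The number of days d is 1 for anagrelide alone and 5 to 9 for the combination.

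**Formulas for the share of subjects with at least one event.**

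- Any TEAE: 1 − (1−a)(1−h)^d.
- Any TEAE, half of events after 24 h captured: 1 − (1−a)(1−h)(1−0.5h)^(d−1).
- Related TEAE: replace h by rh in either formula.

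| Case | Values | Alone | Combination | Ratio | Extra of 20 |
|---|---|---|---|---|---|
| Any, low end | a=0.40, h=0.01, d=5 | 40.6% | 42.9% | 1.06 | 0.47 |
| Any, high end | a=0.20, h=0.05, d=9 | 24.0% | 49.6% | 2.07 | 5.12 |
| Any, half captured, low end | a=0.40, h=0.01, d=5 | 40.6% | 41.8% | 1.03 | 0.24 |
| Any, half captured, high end | a=0.20, h=0.05, d=9 | 24.0% | 37.9% | 1.58 | 2.79 |
| Related, low end | r=0.10, a=0.40, h=0.01, d=5 | 40.06% | 40.30% | 1.01 | 0.05 |
| Related, high end | r=0.25, a=0.20, h=0.05, d=9 | 21.0% | 28.6% | 1.36 | 1.51 |
| Related, half captured, high end | r=0.25, a=0.20, h=0.05, d=9 | 21.0% | 24.9% | 1.18 | 0.77 |

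The last row is 1 − 0.8 × 0.9875 × 0.99375^8 = 0.249.

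**Direction.** The Day 8 acute risk that would cancel the gap is 1 − (1−a)(1−h)^(1−d). At a = 0.40 and h = 0.01 this is 0.375 for d = 5 and 0.350 for d = 9. A fall in acute risk of 2.5 to 5 percentage points at the second exposure would remove the difference.

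**After the fix.** With 0 to 24 h after each anagrelide dose, both columns cover 24 h and both are in-house.

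**The case against.** The strongest reply is that nothing here is an error. Assignment to the treatment most recently taken is unambiguous and follows from a single-sequence design in which omeprazole starts a day after anagrelide. The objective is to assess each regimen, safety is descriptive (Protocol 9.9), and no test or decision uses the columns. That stands, and it limits the point to a cheap improvement. It does not make the columns comparable, and the tables invite the comparison.

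Planned outputs also mitigate. For vital signs, SAP 7.3 says: "The number and percentage of subjects with PCI post-baseline values will be tabulated by time point and treatment group". Readings fall at the same 1, 2, 4, 8 and 12 h on Days 1 and 8. ECG results are also shown by time point (SAP 7.4), with a 12 h tracing on both days. Related-TEAE tables and adverse event listings are planned, and dose times are listed (SAP 5.6), so late events can be traced in about 20 subjects where onset time is recorded. This helps in part. Vital signs and ECGs do not show symptoms such as headache or dizziness, and relatedness is judged open-label.

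The upper magnitudes stack unfavourable assumptions: low acute risk, high background, the longest follow-up and full capture after discharge. That is also fair.

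A reader might take SAP 5.5 as confirming the window, since it runs the last treatment, for medications, "or in the case of the last treatment, until the end of the" follow-up period. It should not be used that way. The same section excludes any medication started after the date of the last dose, so it does not parallel the adverse event rule.

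A reader might also infer that no equal-window table is planned anywhere. The table shells could not be checked, so the statement covers the SAP text only.

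**Conclusion.** The point holds, with low-to-moderate importance. The unequal windows follow directly from SAP 7.1 and the protocol's follow-up. The SAP text neither labels them nor offsets them.

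The size is unknown. On the assumed rates, the extra subjects in the combination column range from under 1 to about 5 of 20 for any TEAE. For related TEAEs they stay under 1 of 20 if half of events after 24 h are captured, and reach about 1.5 of 20 with full capture.

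Two stronger readings are tempting and are not supported. One is that the combination percentage is inflated in proportion to its window, 5 to 9 times as long. Events close to the dose enter both columns and capture falls after discharge, so the ratio under these assumptions is at most 2.07. The other is that the combination must look worse. That direction requires no omeprazole or period effect, and a modest fall in acute risk would cancel it. No primary pharmacokinetic conclusion is touched.

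**What to change.** Keep every planned table. Then:

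- Footnote the by-treatment TEAE tables with the window lengths: about 24 h, 6 days, and 5 to 9 days (Day 8 dose to follow-up contact).
- Add to SAP 7.1 one descriptive table of TEAEs with onset within 24 h of the anagrelide dose on Day 1 (and before the Day 2 omeprazole dose) and on Day 8. Use it when describing the combination next to anagrelide alone, and state that period effects remain.
- Show combination events starting after 24 h separately. Note that delayed events after the Day 1 dose are counted under omeprazole alone.
- List events on Days 2, 8 and 9 that lack an onset time and cannot be placed relative to a dose as indeterminate. An untimed Day 8 event, for example, may have started before the dose and so belong to omeprazole alone.

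If the table shells already contain such a table, a cross-reference in SAP 7.1 is enough.

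The cost is a footnote, a few sentences and one extra table. The table depends on recorded onset times. Dose times are captured (Protocol 6.5), but Protocol 8.1.1 asks only for event start and stop dates, so the indeterminate list may not be empty.
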